10.3.5 Physical Examination

Participants with abnormal post-dose physical examination results will be listed by treatment group and by scheduled time points.

10.4 Other Analyses

10.4.1 Pharmacokinetic Analyses

Data will be listed for all patients with available plasma concentrations in the SPH3127 group. Patients will be excluded from the PK analysis if their data do not allow for accurate assessment of the PK (e.g., missing information of dosing and sampling times; concentration data not sufficient for PK parameter calculation).

All plasma concentrations below the lowest quantifiable concentration or missing data will be labeled as such in the concentration data presentations. Concentrations below the lower quantifiable concentration will be treated as zero in the summary statistics. All patients and samples excluded from the analysis will be clearly documented in the Clinical Study Report.

For each dose, descriptive statistics (including means, median, SDs and coefficient of variation [CVs]) will be calculated for the plasma concentrations at each sampling time and for PK parameters of SPH3127 (e.g., C_{max} , T_{max} , AUC_{last} , AUC_{inf} , $t_{1/2}$, CL/F, and Vz/F. Additional PK parameters may be determined, as appropriate.

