1.3.3 Efficacy and Pharmacodynamics in Humans

SPH3127 has a significantly longer pharmacodynamic than pharmacokinetic $t_{1/2}$ with significantly reduced plasma renin activity (PRA) with near complete inhibition within \sim 30 min of administration and full recovery at 48 hours with only the lowest doses. With repeated doses, PRA suppression is maintained at 70-90%.

As expected from its mechanism of action, SPH3127 produced reductions in both systolic and diastolic blood pressure in all clinical trials. Based on the results of a Phase 2a study in essential hypertension patients, a daily oral dose of 100 mg SPH3127 will be evaluated in future trials of its safety and effectiveness in essential hypertension. A dose of 50 mg QD or BID will be investigated for safety and efficacy in this trial (i.e., ulcerative colitis) to minimize the effects of SPH3127 on blood pressure and to evaluate the relative importance of dose and half-life on therapeutic activity.

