2.2 Secondary

To investigate the pharmacokinetics and pharmacodynamics of daily oral administration of SPH3127 (50 or 100 mg total daily dose) or placebo for 8 weeks in patients with mild-to-moderate ulcerative colitis.

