7.17 SPH3127 Pharmacokinetics

Blood samples (3 mL/time point) will be collected once at each time point (-10" predose, 15", 30", 1', 2', 4', 8') for PK analysis into anticoagulant tubes containing EDTA-K₂ and centrifuged for 15 min. The pretreated PK plasma samples will be frozen and sent for determination of SPH3127 levels. Sample collection will occur over 8 hours at the study site on Days 1, 28 and 56.

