8.3 Dose and Administration

A total of 30 eligible patients will be randomly assigned to one of three treatment arms (10 subjects per treatment group):

- Treatment A: 50 mg SPH3127 (given as one 50 mg tablet in the morning and one placebo tablet in the evening) PO daily for 8 weeks;
- Treatment B: 100 mg SPH3127 (given as one 50 mg tablet in the morning and one 50 mg tablet in the evening) PO daily for 8 weeks;
- Treatment C: Matching placebo tablets PO daily (one tablet in the morning and one tablet in the evening) for 8 weeks.

All randomized subjects will have the opportunity to enter an active treatment extension after the last main study visit (Day 56). Medication will be dispensed at 8-week intervals in the same 2-week blister packs as the main study for an additional 10 months in the active treatment extension. Those subjects receiving Treatment A (50 mg SPH3127 total daily dose) and who choose to enter the extension will continue on Treatment A in a blinded manner (will not know SPH3127 dose). Those subjects receiving Treatment B (100 mg SPH3127 total daily dose) and who choose to enter the extension will continue on Treatment B in a blinded manner (will not know SPH3127 dose). Those subjects receiving Treatment C (placebo) and who choose to enter the extension will be

randomized to receive Treatment A or Treatment B in a blinded manner (will not know SPH3127 dose).

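### Does the PK section need to name a dosing-interval AUC and a CL/F formula for Days 28 and 56?

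*Combined protocol and SAP*

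**What the plan says.** Section 10.4.1 of the protocol plans descriptive statistics for each dose; they "will be calculated for the plasma concentrations at each sampling time and for PK parameters of SPH3127". The examples are Cmax, Tmax, AUClast, AUCinf, half-life, CL/F and Vz/F. The section closes with an open clause: "Additional PK parameters may be determined, as appropriate". It does not assign parameters to days and gives no formula for CL/F. Patients whose data do not allow accurate PK assessment are excluded, for instance for "missing information of dosing and sampling times". On low values it states: "Concentrations below the lower quantifiable concentration will be treated as zero in the summary statistics".

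Section 7.17 fixes the sampling: "Sample collection will occur over 8 hours at the study site on Days 1, 28 and 56", from 10 minutes before the morning dose to 8 hours after it. Under section 8.3, Treatment B is "given as one 50 mg tablet in the morning and one 50 mg tablet in the evening"; Treatment A has the same morning tablet and a placebo in the evening. PK and PD form the secondary objective (section 2.2). Section 1.3.3 says that the two regimens are there partly "to evaluate the relative importance of dose and half-life on therapeutic activity". Section 10.1 plans statistical comparisons of the individual and pooled doses with placebo only.

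**The concern.** The arms differ only in the evening dose, and the evening dose is never sampled directly. On Days 28 and 56 both arms are sampled for 8 hours after an identical 50 mg dose, so AUClast is at most AUC0-8 for one morning dose. The evening dose shows only as carry-over.

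Read carelessly, the AUC tables would suggest that 100 mg a day gives barely more exposure than 50 mg a day. AUCinf is a single-dose quantity. Used at steady state, it credits the morning dose with drug left over from the evening before, and Dose/AUCinf then understates clearance, more so in the twice-daily arm. At stake would be the description of exposure under a secondary objective, in a trial whose regimens were chosen to separate dose from half-life.

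**Working it through.** The documents give no exposure ratio to reproduce, so the size has to be derived.

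**Inputs from the documents.** Half-life T of 3 to 6 h after single doses and about 4 h on repeat dosing, with linear kinetics (1.3.2). Sampling at 10 min pre-dose, then 0.25, 0.5, 1, 2, 4 and 8 h (7.17). Regimens from 8.3.

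**Assumptions.** One compartment at steady state. The gap g from the evening dose to the next morning dose is not stated; 12 h is taken as central and 10 to 16 h as the range.

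**Consistency check.** Once-daily accumulation is 1/(1 − 2^(−24/T)) = 1.004, 1.016 and 1.067 for T = 3, 4 and 6 h. This agrees with the protocol's report of essentially no accumulation.

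**Closed forms (instant absorption), Days 28 and 56**

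- AUC0-8, B/A = 1 + 2^(−g/T). At g = 12: 1 + 2^(−4) = 1.06, 1 + 2^(−3) = 1.125, 1 + 2^(−2) = 1.25 for T = 3, 4, 6 h.
- Pre-dose concentration, B/A = 1 + 2^((24−g)/T). At g = 12: 17, 9 and 5.
- Dose/AUCinf relative to true CL/F, arm B at g = 12: 1 − 2^(−12/T) = 0.94, 0.875, 0.75, so 6%, 12.5% and 25% low.
- The same in arm A: 1 − 2^(−24/T), so 0.4%, 1.6% and 6% low.

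**With absorption and the protocol's sampling times** (absorption rate 5/h assumed, terminal slope from the last three points, linear-up/log-down), g = 12:

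| | T = 3 h | T = 4 h | T = 6 h |
|---|---|---|---|
| AUC0-8, B/A | 1.067 | 1.132 | 1.261 |
| Dose/AUCinf error, B | −5.9% | −12.5% | −25.2% |
| Dose/AUCinf error, A | +0.4% | −1.1% | −6.1% |
| Dose/AUCinf error, Day 1 | +0.8% | +0.6% | +0.4% |

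Over g = 10 to 16 h, the AUC0-8 ratio runs from 1.03 to 1.33 and the arm B error from −2% to −29%.

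**Daily exposure from what is already named.** Day 1 follows a first dose, so AUCinf and Dose/AUCinf are proper there (last row). Daily exposure at steady state is daily dose divided by CL/F. With the same clearance in both arms, (100/CL)/(50/CL) = 2. This needs linearity and clearance that does not change with time.

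**What a named interval AUC would add.** With only a morning profile, AUC0-24 in arm B would be 2 × AUC0-tau. The B/A ratio is then near 2 largely by construction (1.90 to 2.13 over the same grid). CL/F as Dose/AUC0-tau would be within about 6% of true in arm B, but only if the clock time of the home evening dose is known. With the pre-dose sample simply labelled 12 h, at T = 4 h and g = 16 h, CL/F is 10% too high, against 7% too low from AUCinf.

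**Noise.** In a simulation with 10 per arm, T = 4 h, and assumed log-SDs of 0.30 for clearance, 0.25 for volume and 0.10 for assay, the B/A ratio of CL/F from AUCinf had median 0.88 and a 5th to 95th percentile range of 0.66 to 1.15.

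**The case for a change.** The best case for a change is that PK is a stated objective, that the regimens are meant to contrast dose with half-life, and that one added sentence would settle which AUC and which CL/F apply on which day. The named repeat-dose outputs do miss the two-fold daily difference on both sides: AUC0-8 and Cmax ratios are about 1.1, and the pre-dose ratio is about 9. Noise does not hide this. In the same simulation AUC0-8 B/A ran from 0.96 to 1.35 and daily AUC B/A from 1.62 to 2.50, which do not overlap.

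That much stands: AUClast on Days 28 and 56 is a per-morning-dose measure and must not be read as daily exposure. The rest does not carry a change. The section prescribes no wrong calculation; the CL/F bias appears only if an analyst chooses a single-dose formula at steady state. Using a dosing-interval AUC there is ordinary practice, and the open clause allows it. The claim that nothing named conveys daily exposure overlooks Day 1. The aim in 1.3.3 concerns therapeutic activity, which is judged from outcomes by arm, not from an estimated exposure ratio. The worry that unquantifiable values would enter an AUC as zero also goes beyond the text, which applies that rule to summary statistics.

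**Conclusion.** No change to the plan is needed. The figures are correct under the stated model: on Days 28 and 56, AUC0-8 B/A is about 1.13 (1.07 to 1.26 for half-lives of 3 to 6 h at a 12 h gap), and Dose/AUCinf would put CL/F about 12% (6 to 25%) low in the twice-daily arm. They describe what a careless choice within an open list would produce, not what section 10.4.1 requires.

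The effect is confined to description. No comparison between the active arms is planned, and the CL/F shift lies within between-patient noise at 10 per arm. Day 1 AUCinf and CL/F are within 1% of true in the same model and give the two-fold daily ratio under the linearity the protocol reports. Where the previous dose time is missing and PK cannot be assessed accurately, the existing exclusion already applies. The sizes rest on a one-compartment model, an assumed overnight gap and assumed variability; the conclusion does not depend on their exact values.

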10.4.2 Biomarker Analyses

UC tissue and plasma cytokine assays will be performed using standardized multiplex assays for each collection timepoint from all subjects. Fecal calprotectin will be determined in a standardized chemiluminescence assay. Descriptive statistical methods will be used to summarize the data from these exploratory measures.

10.4.3 Modified Mayo Clinical Score, UC-100, Robarts Histopathology Index

Descriptive statistical methods will be used to analyze the data from Modified Mayo Clinical Score and Mayo subscales, UC-100, and Robarts Histopathology Index.

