I have read the protocol, including all appendices, and I agree that it contains all of the necessary information for me and my staff to conduct this study as described. I will conduct this study as outlined herein, in accordance with the regulations stated in the Federal Code of Regulations for Good Clinical Practices and International Conference on Harmonization guidelines, and will make a reasonable effort to complete the study within the time designated.

I will provide all study personnel under my supervision copies of the protocol and any amendments, and access to all information provided by SPHBio or specified designees. I will discuss the material with them to ensure that they are fully informed about SPH3127 and the study.

Principal Investigator	Name (printed)	Signature
Date	Site Number	

STUDY SUMMARY

Title: A Double-Blind, Placebo-Controlled Trial to Investigate the

Pharmacokinetics, Pharmacodynamics, Safety, and Tolerability of SPH3127 in Patients with Mild-to-Moderate Ulcerative Colitis

Rationale: Recently, an association has been made between the renin-angiotensin

system (RAS) and the development of colitis. The RAS is well known to regulate blood pressure and fluid and electrolyte balance, as well as systemic vascular resistance. Circumstantial evidence also suggests an involvement of the RAS in the pathogenesis of colitis. For example, increased colonic mucosal angiotensin I and II concentrations were reported in Crohn's disease (CD) patients with active inflammation, and in human biopsies, pro-inflammatory cytokines were suppressed in patients with inflammatory bowel disease who were on angiotensin receptor blocker (ARB) therapy compared to patients not receiving ARB therapy. In animal studies, renin inhibitors like SPH3127 have shown activity in rodent models of colitis. Consistent with an involvement of the RAS, SPH3127 improved physical measures of colitis (e.g., colon length, colon weight) and reduced colon levels of inflammatory cytokines (IL-1β, IL-6, IL-17A and TNF- α) in this model. This study seeks to establish the safety and tolerability SPH3127 in patients with mild-to-moderate ulcerative colitis and to provide initial indications of efficacy.

Target Population:

Mild-to-moderate ulcerative colitis patients

Number of Subjects:

30 subjects - 50 mg SPH3127 QD: 50 mg SPH3127 BID: Placebo, 1:1:1

randomization

Objectives: To investigate the safety and tolerability of daily oral administration of

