4 STUDY PLAN

4.1 Study Design

In this double-blind, placebo-controlled, multi-center trial, patients ≥ 18 to ≤ 70 years of age with mild-to-moderate ulcerative colitis (UC) will be randomly assigned to daily oral treatment with SPH3127 (given as one 50 mg tablet in the morning and one placebo tablet in the evening, or given as one 50 mg tablet in the morning and one 50 mg tablet in the evening (100 mg total daily dose) or matching placebo tablets (one placebo tablet in the morning and evening) for 8 weeks. The objective of this study is to assess the safety and tolerability of SPH3127. In addition, the PK and PD effects of SPH3127 will be

assessed; PD effects will be assessed through plasma and colitis lesion biomarkers and validated measures of disease activity (e.g., modified Mayo Score (MMS), UC-100, Robarts Histology Index (RHI) and fecal calprotectin).

A total of 30 eligible patients will be randomly assigned to one of three treatment arms (10 subjects per treatment group):

- Treatment A: 50 mg SPH3127 (given as one 50 mg tablet in the morning and one placebo tablet in the evening) PO daily for 8 weeks
- Treatment B: 100 mg SPH3127 (given as one 50 mg tablet in the morning and one 50 mg tablet in the evening) PO daily for 8 weeks
- Treatment C: Matching placebo tablets PO daily (given as one tablet in the morning and one tablet in the evening) for 8 weeks

A patient will be considered enrolled in the trial once they have provided signed informed consent, met all inclusion/exclusion criteria, been randomized to treatment and received at least one dose of study drug. Baseline measurements will be taken at screening or on Day 1 prior to the first treatment.

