5.3 Inclusion Criteria

- 1. Signed Informed Consent Form (ICF);
- 2. Adult males and females \geq 18 to \leq 70 years of age on the day of signing the ICF.
- 3. A diagnosis of UC (documented or confirmed at screening) will be eligible provided they have mild-to-moderate active UC extending ≥ 15 cm from the anal verge.
- 4. At screening/baseline, a Modified Mayo Clinic Score (MMCS) from 4-9, a rectal bleeding subscore ≥ 1, and a Mayo Clinic Endoscopic Subscale (MCES) score ≥ 2 determined by central reading.
- 5. Patient has a negative urine drug screen (e.g., amphetamines, barbiturates, benzodiazepines, cannabis, cocaine, opiates, methadone) at Screening.
- 6. Patient has a negative alcohol breath test at Screening.
- 7. Female patients who have a negative pregnancy test at Screening and who agree to use adequate birth control methods throughout the entire study (and extension, if applicable) or who is post-menopausal (i.e., amenorrhea ≥ 1 year) or who have been surgically sterilized.
- 8. Male patients with partners of child-bearing potential who agree to use adequate birth control methods throughout the entire study (and extension, if applicable) or who have been surgically sterilized.

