6.2.2 Baseline and Randomization Visit (Day 1)

On Day 1, all Events will be completed, except PK and plasma biomarkers, prior to oral dosing. PK and plasma biomarker samples will be collected at the defined intervals \pm 5 min.

The following procedures will be performed on **Day 1** (pre-dose):

- Randomization to treatment (can be performed up to 2 days prior to Day 1);
- Physical examination;
- Vital signs assessment (systolic and diastolic blood pressure (seated), heart rate, temperature (-10" pre-dose);
- ECG;
- Clinical laboratory assessments;
- Urine pregnancy test;
- Concomitant medications;
- Stool frequency (from diary);
- Rectal bleeding (from diary);
- PK (-10" pre-dose);
- Plasma biomarkers (-10" pre-dose);
- Dispense medication (2-week blister packs) and drug accountability Take first morning oral dose on-site.

The following procedures will be performed on **Day 1** (post-dose):

- Vital signs assessment (systolic and diastolic blood pressure (seated), heart rate, temperature (30", 2', 4', 8');
- PK (15", 30", 1', 2', 4', 8');
- Plasma biomarkers (1', 2', 4', 8').

6.2.3 *Visit Day 14* (\pm 2 days)

Day 14 is primarily a safety and compliance check.

The following procedures will be performed on **Day 14 (pre-dose)**:

- Physical examination;
- Vital signs assessment (systolic and diastolic blood pressure (seated), heart rate, temperature);
- Concomitant medications;
- Adverse events;
- Stool frequency (from diary);
- Rectal bleeding (from diary);
- Dispense medication (2-week blister packs) and drug accountability Take morning oral dose on-site.

6.2.4 *Visit Day 28* (\pm 2 days)

The events at the site visit on Day 28 are similar to the Events on Day 1.

The following procedures will be performed on **Day 28 (pre-dose)**:

- Physical examination;
- Vital signs assessment (systolic and diastolic blood pressure (seated), heart rate, temperature (-10" pre-dose));
- Clinical laboratory assessments;
- Concomitant medications:
- Adverse events;
- Fecal calprotectin (stool collection);
- Stool frequency (from diary);
- Rectal bleeding (from diary);
- PK (-10" pre-dose);
- Plasma biomarkers (-10" pre-dose);

• Dispense medication (2-week blister pack x 2) and drug accountability – Take morning oral dose on-site.

The following procedures will be performed on **Day 28 (post-dose)**:

- Vital signs assessment (systolic and diastolic blood pressure (seated), temperature (30", 2', 4', 8');
- PK (15", 30", 1', 2', 4', 8');

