10 STATISTICS

10.1 General Procedures

Descriptive statistical methods will be used to summarize the data from this exploratory study, with the term descriptive statistics referring to the number of subjects (n), mean, median, standard deviation (SD), minimum, and maximum for continuous data and frequencies and percentages for categorical data. Analyses will be performed at both the end of the main 8-week study and the active treatment extension. All statistical testing will be 2-sided and performed using a significance (α) level of 0.05. Statistical comparisons to placebo will be to the individual and pooled doses of SPH3127. The

statistical analyses will be conducted with the SAS software package version 9.1.3 or higher (SAS Institute, Inc, Cary, North Carolina).

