10.2 Sample Size

No formal sample size and power calculations were made for this exploratory study.

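### Week 8 MMCS, UC-100 and Robarts scores are to be compared with placebo at 10 per arm, but no planned analysis uses the baseline score as a covariate; a baseline ANCOVA would recover precision at almost no cost

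*Combined protocol and SAP*

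**What the plan says.** Section 10.1 calls the study exploratory and the methods descriptive, but it also plans tests: "All statistical testing will be 2-sided and performed using a significance (α) level of 0.05", and "Statistical comparisons to placebo will be to the individual and pooled doses of SPH3127". Section 10.4.3 covers the three scores in one sentence: "Descriptive statistical methods will be used to analyze the data from Modified Mayo Clinical Score and Mayo subscales, UC-100, and Robarts Histopathology Index". No section names a test, a model or a covariate for them.

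Baseline is not absent from the plan. The endpoint list in the Study Summary includes change in the Robarts index and improvement in UC-100. Section 10.4.4 defines clinical response by each patient's fall in MMCS from baseline. By contrast, clinical remission, endoscopic improvement (MCES of 1 or less) and endoscopic remission (MCES of 0) are Week 8 states with no reference to baseline.

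On size and allocation, section 4.1 gives 30 patients, 10 per arm, and the Study Summary gives "30 subjects - 50 mg SPH3127 QD: 50 mg SPH3127 BID: Placebo, 1:1:1" randomisation. Section 6.2.2 adds only the timing. The method of randomisation (blocks, strata, minimisation) is not described. Entry requires an MMCS of 4 to 9 and an "Mayo Clinic Endoscopic Subscale (MCES) score ≥ 2 determined by central reading", so entry MCES is 2 or 3. Section 10.2 states: "No formal sample size and power calculations were made for this exploratory study".

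**The concern.** The schedule in section 4.2 provides a pre-treatment value of all three scores for every patient. Entry thresholds select active disease, so some fall by Week 8 is expected from regression to the mean alone, and a group that happens to start higher can be expected to fall further. With 10 per arm, chance differences in starting severity are common. Raw Week 8 means favour the arm that started milder, and raw changes favour the arm that started more severe. Neither summary removes the imbalance, so subtracting baseline does not settle the matter.

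The Study Summary says the trial is to give initial indications of efficacy, and section 1.1 calls it proof of concept. There will be one realised dataset, and a development decision may rest partly on its placebo contrasts. Precision that the collected data could supply should not be left unused.

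**Working it through.** The plan gives no effect size, SD or power, so there is no figure of its own to reproduce. The arithmetic 3 × 10 = 30 agrees.

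**Inputs from the protocol:** 10 per arm (section 4.1); contrasts of 10 v 10 and 20 v 10 (section 10.1); two-sided α of 0.05 (section 10.1); entry MCES of 2 or 3 (section 5.3).

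**Assumed, because the documents give no value:** baseline to Week 8 correlation r of 0.3 to 0.7; k, the ratio of baseline SD to Week 8 SD, of 0.5 to 1; 9 to 15 of the 30 patients entering with MCES 3; normal scores.

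**1. Chance baseline gap.** The SD of the difference in baseline means, in baseline SD units, is √(1/n₁ + 1/n₂).
- One dose v placebo: √(0.1 + 0.1) = 0.447. P(|gap| > 0.5 SD) = 2·P(Z > 0.5/0.447) = 0.26.
- Pooled v placebo: √(0.05 + 0.1) = 0.387. P(|gap| > 0.5 SD) = 2·P(Z > 0.5/0.387) = 0.20.

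**2. Carry-over of a gap d (k = 1).** The expected shift is r·d in raw Week 8 means, (r − 1)·d in changes, and 0 after ANCOVA. For d = 0.5 SD:

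| r | raw Week 8 | change |
|---|---|---|
| 0.3 | +0.15 | −0.35 |
| 0.5 | +0.25 | −0.25 |
| 0.7 | +0.35 | −0.15 |

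**3. Type I error (simulation, 100,000 trials of 10 v 10, k = 1).** Overall it is 0.049 to 0.051 for raw, change and ANCOVA alike. Among trials with a baseline gap above 0.5 SD:

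| r | raw | change | ANCOVA |
|---|---|---|---|
| 0.3 | 0.067 | 0.109 | 0.049 |
| 0.5 | 0.094 | 0.097 | 0.049 |
| 0.7 | 0.135 | 0.078 | 0.048 |

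**4. Variance of ANCOVA relative to raw Week 8 means.** The large-sample ratio is 1 − r². Estimating the slope multiplies it by 1 + 1/(ν − 2), where ν is the within-arm degrees of freedom: 1 + 1/25 = 1.04 with all three arms in the model (ν = 27), and 1 + 1/16 = 1.0625 with two (ν = 18).
- r = 0.3: 0.91 × 1.04 = 0.95; 0.91 × 1.0625 = 0.97.
- r = 0.5: 0.75 × 1.04 = 0.78; 0.75 × 1.0625 = 0.80.

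**5. Variance of ANCOVA relative to change scores.** The large-sample ratio is (1 − r²)/(1 + k² − 2rk).

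| k | r = 0.3 | r = 0.5 |
|---|---|---|
| 1 | 0.91/1.40 = 0.65 | 0.75/1.00 = 0.75 |
| 0.75 | 0.91/1.1125 = 0.82 | 0.75/0.8125 = 0.92 |
| 0.5 | 0.91/0.95 = 0.96 | 0.75/0.75 = 1.00 |

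With the factor 1.04, the k = 1 row becomes 0.68 and 0.78. In patients, k = 1 is worth 1/0.75 to 1/0.65, or about 33% to 54% more per arm before that factor. For k of 0.5 to 0.75 the gain is 1/1.00 to 1/0.82, or about 0% to 22%. At r = k = 0.5 the slope costs slightly more than it returns (1.00 × 1.04 = 1.04).

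**6. Entry MCES.** If 12 of 30 patients enter with MCES 3 and allocation is an unstratified split into 3 × 10, exact enumeration gives an 11% chance that one given dose and placebo differ by 4 or more such patients (9% for 9 of 30, 12% for 15 of 30). For any two of the three arms the chance is 25%, but that counts dose v dose, which section 10.1 does not list as a comparison.

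**The case against.** The strongest reply is that this is an exploratory study with safety and tolerability as its primary objective, no power calculation and an efficacy analysis declared descriptive. Unadjusted summaries are then a legitimate choice, and randomisation already makes the contrasts unbiased. This stands as far as validity goes: the issue is precision and the reading of one realised result. It does not remove the case for adjustment, because section 10.1 plans formal comparisons and the covariate is already collected.

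The size of the gain is also open to challenge. Entry limits restrict the baseline range, while Week 8 scores can fall to the bottom of the scale, so the baseline SD may be the smaller one and the advantage over change scores may shrink to nothing. That stands, and it is why a range is shown.

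Three stronger readings are tempting, and the documents support none of them.
- A reader might infer that the scores are compared with no reference to baseline. Robarts change, UC-100 improvement and MMCS response all refer to it.
- A reader might infer that baseline imbalance passes in full into the contrasts or invalidates the tests. Only a fraction carries over, and overall type I error is unaffected; the raised rates in step 3 apply only to trials that happen to have a gap above 0.5 SD.
- A reader might infer that allocation is unstratified. The protocol is silent on the method, and silence does not show that.

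**Conclusion.** The point holds as a matter of efficiency. Placebo comparisons are planned, baseline scores are collected, and no analysis of MMCS, UC-100 or Robarts uses them as a covariate. About one single-dose contrast in four will start with a severity gap above 0.5 SD, and about one in five pooled contrasts; these probabilities need only the arm sizes and approximate normality of the means.

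The gain from adjustment rests on assumed correlations and SD ratios. Against raw Week 8 means it is small at r = 0.3 (variance ratio 0.95 to 0.97) and useful at r = 0.5 (about 0.80). Against change scores it is substantial if the SDs are equal (0.65 to 0.68 at r = 0.3, 0.75 to 0.78 at r = 0.5) and slight or nil if the baseline SD is half to three quarters of the Week 8 SD (0.82 to 1.00). The main benefit is that the estimate no longer depends on which arm happened to start worse.

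Imbalance in entry MCES is a lesser matter. A gap of 4 or more MCES 3 patients between one dose and placebo has a probability of about 11% under unstratified allocation, and the protocol does not say whether allocation is unstratified.

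**What to change.** Add to section 10.4.3: for Week 8 MMCS, UC-100 and Robarts, each placebo difference (each dose, and the pooled doses) is estimated by ANCOVA with treatment and that score's own baseline value, one common slope, and reported as an adjusted mean difference with 95% CI beside the descriptive tables. Name the baseline value to be used: stool frequency and rectal bleeding are recorded by patient report at screening and from the diary on Day 1, and section 4.1 allows baseline measurements at either time. Tabulate baseline severity by arm.

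The cost is one degree of freedom per model and no new data.

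Separately, state the randomisation method. Stratifying by centrally read entry MCES (2 or 3) is optional at this size, and the ANCOVA does not depend on it.
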